5.1 Mini-Mental State Examination (MMSE)

The MMSE (Folstein 1975) consists of the following 5 components:

- Orientation to time and place (2 items)
- Registration of 3 words (1 item)
- Attention and calculation (1 item)
- Recall of 3 words (1 item)
- Language (6 items)

The scores from the 5 components are summed to obtain the overall MMSE total score. The MMSE total score can range from 0 to 30, with higher scores indicating better mental status.

Although available in the raw data, the MMSE total score will be recalculated. If a subject has 1 missing item, the following algorithm will be used to compute the total score: Total score = [(total score from completed items) / (maximum total score for completed items)] x (maximum total score [=30] for all items in the scale). The total score is then rounded to the next highest integer. If there is more than 1 missing item, the total score will be considered missing at that time point.

Changes from baseline for the recalculated MMSE total score will be summarized at each scheduled timepoint (Days 6 and 33) (Table 14.2.1).

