5 STUDY ENROLLMENT AND WITHDRAWAL

5.1 INCLUSION CRITERIA

In order to be eligible for inclusion, all subjects must meet the following criteria:

1. Male or female, aged 60-95 years (inclusive).
2. Diagnosis of AD based upon the National Institute on Aging-Alzheimer's Association (NIA-AA) Criteria.
3. MMSE Score 0 – 10 (inclusive).
4. Modified Hachinski Ischemia Scale (MHIS) score of ≤ 4 .
5. If on medications for cognition (e.g., rivastigmine, galantamine, donepezil, memantine), must be on stable dosage for at least 8 weeks prior to Baseline.

6. If on daily antidepressant medications and/or benzodiazepines and/or typical or atypical antipsychotics, must be on stable dosage for 8 weeks prior to Baseline. If on prn dosing with atypical antipsychotics and/or benzodiazepines, these should not be given within 24 hours before each day of cognitive and other ratings (V1, V2, V8, V9, V10).
7. The subject (with support of a caregiver and/or staff) must be able to follow the study protocol, receive the treatment in the established timeframe, and continue during the follow-up interval.
8. The subject must be sufficiently fluent in English and have visual and auditory acuity sufficient to be capable of reliably completing all study assessments.
9. Provided a signed and dated informed consent form (subject's legal representative) in accordance with local regulations/guidelines/IRB.
10. Adequate renal function as defined by estimated glomerular filtration rate (eGFR) ≥ 45 mL/min/1.73 m² using the Modification of Diet in Renal Disease (MDRD) study equation and no microalbuminuria.
11. Systolic ejection fraction of $\geq 55\%$ on trans-thoracic echocardiogram.

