Appendix 1. The Mini-Mental Status Examination

Instructions for Administration and Scoring

Orientation (10 points):

- Ask for the date. Then specifically ask for parts omitted (e.g., “Can you also tell me what season it is?”). One point for each correct answer.
- Ask in turn, “Can you tell me the name of this facility (town, county, etc.)?” One point for each correct answer.

Registration (3 points):

- Say the names of three unrelated objects clearly and slowly, allowing approximately one second for each. After you have said all three, ask the patient to repeat them. The number of objects the patient names correctly upon the first repetition determines the score (0-3). If the patient does not repeat all three objects the first time, continue saying the names until the patient is able to repeat all three items, up to six trials. Record the number of trials it takes for the patient to learn the words. If the patient does not eventually learn all three, recall cannot be meaningfully tested.
- After completing this task, tell the patient, “Try to remember the words, as I will ask for them in a little while.”

Attention and Calculation (5 points):

- Ask the patient to begin with 100 and count backward by sevens. Stop after five subtractions (93, 86, 79, 72, 65). Score the total number of correct answers.
- If the patient cannot or will not perform the subtraction task, ask the patient to spell the word “world” backwards. The score is the number of letters in correct order (e.g., dlrow=5, dlorw=3).

Recall (3 points):

- Ask the patient if he or she can recall the three words you previously asked him or her to remember. Score the total number of correct answers (0-3).

Language and Praxis (9 points):

- Naming: Show the patient a wrist watch and ask the patient what it is. Repeat with a pencil. Score one point for each correct naming (0-2).
- Repetition: Ask the patient to repeat the sentence after you (“No ifs, ands, or buts.”). Allow only one trial. Score 0 or 1.
- 3-Stage Command: Give the patient a piece of blank paper and say, “Take this paper in your right hand, fold it in half, and put it on the floor.” Score one point for each part of the command correctly executed.

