- Reading: On a blank piece of paper print the sentence, “Close your eyes,” in letters large enough for the patient to see clearly. Ask the patient to read the sentence and do what it says. Score one point only if the patient actually closes his or her eyes. This is not a test of memory, so you may prompt the patient to “do what it says” after the patient reads the sentence.
- Writing: Give the patient a blank piece of paper and ask him or her to write a sentence for you. Do not dictate a sentence; it should be written spontaneously. The sentence must contain a subject and a verb and make sense. Correct grammar and punctuation are not necessary.

- Copying: Show the patient the picture of two intersecting pentagons and ask the patient to copy the figure exactly as it is. All ten angles must be present and two must intersect to score one point. Ignore tremor and rotation.

Interpretation of the MMSE

Method	Score	Interpretation
Single Cutoff	<24	Abnormal
Range	<21	Increased odds of dementia
	>25	Decreased odds of dementia
Education	21	Abnormal for 8 th grade education
	<23	Abnormal for high school education
	<24	Abnormal for college education
Severity	24-30	No cognitive impairment
	18-23	Mild cognitive impairment
	0-17	Severe cognitive impairment

Reference:

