5 EFFICACY

The study is not powered to detect significant changes in cognition, function, ADLs, etc.; however, using available data from analysis of the secondary efficacy endpoints, including changes in scores from baseline, descriptive summaries will be developed. Of particular interest will be the within-subject changes from baseline and their distribution around a null value of zero and a comparison between groups to evaluate any trends in differences between subjects randomized to active and placebo agents.

For analysis purposes, results at early termination visits will not be included in tabulated summaries unless the number of early termination visits is > 5.

Following efficacy endpoints will be analyzed based on both EVAL and PPROT sets.

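### With one MMSE item missing, the prorated total is rounded up, so a missing one-point item earns its full point at every completed-item sum from 1 to 10

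*SAP*

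**What the plan says.** SAP 5.1 and Protocol 7.1.1.1.2 give the same scoring rule. If one item is missing, the sum of the completed items is divided by their maximum and multiplied by 30. Then: "The total score is then rounded to the next highest integer". Beyond one missing item there is no proration: "If there is more than 1 missing item, the total score will be considered missing at that time point".

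The rule will be applied by the analysis programs, because SAP 5.1 states "Although available in the raw data, the MMSE total score will be recalculated". The recalculated total feeds the change from baseline at Days 6 and 33 (Table 14.2.1). SAP 5 says that particular interest lies in "within-subject changes from baseline and their distribution around a null value of zero", together with a descriptive comparison between groups. Entry requires an MMSE score from 0 to 10 (Protocol 5.1, criterion 3).

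**The concern.** Proration assumes that the subject would have done as well on the missing item as on the rest. For someone who scored a few points out of 29, that supports a small fraction of a point on a one-point item. Rounding up turns any such fraction into a whole point. For one-point items the rule therefore stops being proration and scores the undone item as passed. For larger items the rounding can only add or leave unchanged.

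Low scores are where proration supports least credit for a one-point item, so the upward error is largest in exactly the range this trial enrols. What is at stake is the individual change score. An item missing at one visit and not at the other puts the rounding error straight into that subject's change. With about 16 evaluable subjects, single values show in the median, minimum and maximum that SAP 2.6 reports.

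The point concerns the rounding step only. It does not dispute proration or the limit of one missing item.

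**Working it through.** **Inputs**

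- Proration and rounding: SAP 5.1 and Protocol 7.1.1.1.2.
- Score range of interest: 0–10 (Protocol 5.1).
- Item weights: Protocol Appendix 1, which section 17 labels as an example form. Repetition is a one-point item ("Allow only one trial. Score 0 or 1"), as are reading ("Score one point only if the patient actually closes his or her eyes") and copying. Writing is one point by subtraction from the nine language points: 9 − (2 + 1 + 3 + 1 + 1) = 1. Naming is 2. Registration, recall and the three-stage command are 3 each. Attention is 5. The ten orientation points are taken as 5 + 5 over two items (assumption).

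**The plan's own figure.** Appendix 1 gives 10 + 3 + 5 + 3 + 9 = 30. By item: 4 × 1 + 1 × 2 + 3 × 3 + 3 × 5 = 30 over 11 items. Both agree with the maximum of 30 used in the rule.

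**Formula.** With S the completed-item sum and m the maximum of the missing item, the prorated total is p = S × 30/(30 − m). The rounding error is (p rounded up) − p, reading the rule as a ceiling, so that a p already whole is unchanged.

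**One-point item missing (m = 1), p = S + S/29**

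| S | p | Rounded up | Credit supported | Rounding error |
|---|---|---|---|---|
| 1 | 1.034 | 2 | 0.034 | 0.966 |
| 2 | 2.069 | 3 | 0.069 | 0.931 |
| 3 | 3.103 | 4 | 0.103 | 0.897 |
| 4 | 4.138 | 5 | 0.138 | 0.862 |
| 5 | 5.172 | 6 | 0.172 | 0.828 |
| 6 | 6.207 | 7 | 0.207 | 0.793 |
| 7 | 7.241 | 8 | 0.241 | 0.759 |
| 8 | 8.276 | 9 | 0.276 | 0.724 |
| 9 | 9.310 | 10 | 0.310 | 0.690 |
| 10 | 10.345 | 11 | 0.345 | 0.655 |

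The result is S + 1 in all ten rows. The mean error is 1 − 5.5/29 = 0.81. Because p is never whole here, a ceiling and a literal next-integer-above reading give the same totals.

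**All item sizes**

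| Missing item | Mean error, S = 1–10 | Mean error, S = 0–10 | Sums with zero error |
|---|---|---|---|
| 1 point | 0.81 | 0.74 | 0 |
| 2 points | 0.61 | 0.55 | 0 |
| 3 points | 0.49 | 0.44 | 0, 9 |
| 5 points | 0.40 | 0.36 | 0, 5, 10 |

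If each of the 11 items were equally likely to be the missing one (assumption), the mean over S = 1–10 is (4 × 0.810 + 0.607 + 3 × 0.489 + 3 × 0.400)/11 = 0.59.

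**In a change score.** Take a subject who scores 6 on the other items at both visits and fails copying at baseline, for a baseline total of 6. If copying is missing at Day 33, p = 6.21. The unrounded change is +0.21; the plan records +1. If copying is instead missing at baseline and failed at Day 33, the unrounded change is −0.21 and the plan records −1.

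**The case against.** The strongest case against is that this hardly matters. The rule bites only when exactly one item is missing, and neither document suggests how often that will happen. Suppose the 16 or so evaluable subjects split about 11 and 5 (assumption). One affected one-point total then moves a group mean by at most 0.97/11 = 0.09 or 0.97/5 = 0.19; at the equal-weight mean of 0.59 the shifts are 0.05 and 0.12. MMSE is one of five descriptive efficacy scales in a study stated to be unpowered. This stands, and it is why the point is minor.

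Full credit also arises for only four of 11 items, and nothing in the plan says those are the ones likely to be missed. Where the subject really would have passed the item, S + 1 happens to be right. Both are true. Neither makes the rounding step neutral: against the plan's own prorated value, its error is zero or upward, never downward.

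A prespecified rule that keeps an integer scale on integers has some appeal. However, no statistic in SAP 2.6 needs an integer total. Rounding to the nearest integer would not cure the problem either: for one-point items at S = 1–10 it always returns S, a downward error averaging 5.5/29 = 0.19.

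Eligibility gives no extra weight to the concern. Under the ceiling reading, a prorated total rounds to 10 or less exactly when it is already 10 or less, so rounding changes nobody's standing against the 0–10 criterion.

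**Conclusion.** The concern holds. For a missing one-point item and a completed-item sum of 1–10, the rule always awards the full point where proration supports 0.03–0.34. The rounding error is 0.66–0.97 point per affected total, with a mean of 0.81. Across all 11 items, if equally likely to be missing, the mean is 0.59.

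The item-specific figures rest on Appendix 1's point values, and the means give each sum equal weight. The zero-error cases and the figures that include a sum of 0 also rest on reading the rule as a ceiling. Taken literally, the wording would turn a prorated 0 into 1 and 30 into 31, the latter outside the scale.

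The consequence is confined to individual change scores on a descriptive secondary endpoint. No between-arm bias is claimed, and the effect on group means cannot be computed without a missing-item rate. This is a change worth considering, not a threat to the trial's conclusions.

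**What to change.** Delete the rounding sentence from SAP 5.1 and analyse the prorated total unrounded. Leave the rest of the rule as it is, including that more than one missing item makes the total missing. Record the departure in SAP section 8 before database lock, and delete the matching sentence in Protocol 7.1.1.1.2 if the protocol is amended. Doing it through the SAP avoids an amendment, with its IRB approval, for this point alone.

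The cost is small, since the SAP already recalculates the total. There will be an occasional non-integer total, and because SAP 2.6 reports minimum and maximum at the precision of capture, a prorated extreme needs a display note. Deleting the sentence also removes the ambiguity over prorated totals that are already whole. It does not settle how a non-integer screening total is read against the entry criterion; that remains for the sponsor to state.

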7.3.1 SCREENING

Screening Visit (Day -28 to -8)

- Obtain informed consent from the subject's legally authorized representative and informed assent from the subject, if applicable, prior to performing any study-related assessments.
- Assess for probable AD using NIA-AA criteria and administer the MMSE.
- Conduct the MHIS.
- Obtain medical history to determine eligibility based on inclusion/exclusion criteria.
- Collect demographic information.
- Review subject's current and prior medications.
- Collect vital signs, height, and weight.
- Perform the physical exam.
- Perform the 12-lead ECG.
- Collect blood and urine specimens for labs.
- Perform transthoracic echocardiogram.

Note: The Screening Visit may be split to allow sufficient time to complete all required procedures. AEs and concomitant medications should be recorded during split visits, if applicable.

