7.3.2 BASELINE

Baseline Visit (Days -7 to -1)

- Re-review Screening assessments for eligibility.
- Review AEs and concomitant medications.
- Collect vital signs.
- Ensure the subject has had an opportunity to eat a meal or snack prior to administering cognitive and functional assessments.
- Administer cognitive and functional assessments in the following order:

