2.3 Study Phase, Visit, and Day

The study is set up as shown above, along with study phase, visit, and day. In general, the baseline is defined as the last assessment before the first intake of the study medication unless otherwise specified. All scheduled assessments after first administration of study drug will be used.

Repeat/unscheduled assessments will not be used in descriptive statistics or any per-time point analyses but will be shown in listings as applicable. Pre-dose unscheduled assessments will be taken into account for baseline determination and post first dose unscheduled assessments will be taken into account for worst-case determination as applicable.

Reference date refers to the start date of the first study drug administration. All efficacy and safety assessments at all visits will be assigned a day relative to this date. The relative day will be defined as: visit date – reference date + 1 for visits on or after the reference date and visit date – reference date for visits before the reference date. Consequently, there is no 'Day 0' defined.

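### MMSE change from baseline starts from the Screening score used for entry, so zero is not a reliable null value for within-arm or pooled MMSE change

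*SAP*

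**What the plan says.** Inclusion criterion 3 (Protocol 5.1) requires an MMSE of 0 to 10. The only scheduled MMSE before dosing is at Screening, where Protocol 7.3.1 tells sites: "Assess for probable AD using NIA-AA criteria and administer the MMSE". The two windows are "Screening Visit (Day -28 to -8" and "Baseline Visit (Days -7 to -1".

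The Baseline Visit list in Protocol 7.3.2 has SIB, ADCS-ADL-Severe, ADCS-CGIC and NPI or NPI-NH, but no MMSE. Table 15.1 agrees, with MMSE at Visits 1, 8 and 10 only.

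SAP 2.3 gives the general rule: "In general, the baseline is defined as the last assessment before the first intake of the study medication unless otherwise specified". SAP 5.1 specifies no different baseline for MMSE and says only: "Changes from baseline for the recalculated MMSE total score will be summarized at each scheduled timepoint (Days 6 and 33". SAP 2.3 adds: "Pre-dose unscheduled assessments will be taken into account for baseline determination". An unscheduled pre-dose MMSE would therefore replace the Screening score, but none is planned.

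SAP 5 names as one focus of interest "within-subject changes from baseline and their distribution around a null value of zero". The same sentence also names a comparison between groups.

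**The concern.** The score that admits the subject is also the score from which change is measured. When subjects are admitted because a noisy score fell at or below a ceiling, those whose score was low by chance are over-represented, and on average they score higher on retest with no treatment effect. SIB, ADCS-ADL-Severe and NPI are not selected on, and their reference comes from the later Baseline Visit.

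The MMSE change also includes up to four weeks before any infusion. In a progressive disease, decline over that time acts downward. Two non-treatment components of opposite sign and unknown size thus sit inside the quantity that SAP 5 sets against zero.

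The Overall column required by SAP 2.6 pools both arms, so no control subtracts either component there. At stake is how within-arm and pooled MMSE change is interpreted, in a study that Protocol 2.2 expects to lay the groundwork for larger trials.

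**Working it through.** **1. Which score is the baseline.** Scheduled pre-dose MMSE: Visit 1 only (Protocol 7.3.1, 7.3.2, 15.1). Under SAP 2.3, with no exception in SAP 5.1, the baseline is the Visit 1 score, which is also the entry score.

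**2. Intervals.** SAP 2.3 has no Day 0, so the time from Day −a to Day b is a + b − 1 days.

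| Interval | From Screening (Day −28 to −8) | From Visit 2 (Day −7 to −1) |
|---|---|---|
| Untreated time to Day 1 | 8 to 28 | 1 to 7 |
| To nominal Day 6 | 13 to 33 | 6 to 12 |
| To Visit 8 with its window (up to Day 9) | 13 to 36 | 6 to 15 |
| To nominal Day 33 | 40 to 60 | 33 to 39 |

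Untreated time is 8/13 to 28/33 = 62% to 85% of the nominal Day 6 interval, and 8/40 to 28/60 = 20% to 47% of the nominal Day 33 interval. These figures need no assumption beyond the visit windows.

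**3. Selection component.** The documents give no MMSE mean, SD or retest error, so these are assumed: mean μ of the screened pool 5, 8 or 11; true-score SD 4 or 6; independent retest error SD e from 1.0 to 2.5; true score unchanged. With observed SD s = √(SD² + e²) and k = (10.5 − μ)/s,

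E[retest − Screening | Screening ≤ 10] ≈ (e²/s) × φ(k)/Φ(k).

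- Low end (μ 5, SD 4, e 1.0): s = 4.123, k = 1.334, so (1/4.123) × 0.1639/0.9089 = 0.04. Simulation with whole-number scores floored at 0 gives +0.05.
- High end (μ 11, SD 4, e 2.5): s = 4.717, k = −0.106, so (6.25/4.717) × 0.3967/0.4578 = 1.15. Simulation gives about +1.2 (1.15 to 1.17 across runs).

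A second parameterization (pool mean 4 to 12, observed SD 4 to 6, reliability 0.80 to 0.95) gave +0.02 to +1.17. The component was positive in every setting tested.

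**4. Visit 2 as baseline.** With a Visit 2 score that is not used for eligibility, the simulated component is 0.00 to within 0.01 in every setting, given independent retest errors.

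**5. Between-group difference.** With 16 evaluable subjects split 11:5 (mean 8, SD 5, reliability 0.90), the simulated between-arm difference averaged −0.01 while the mean within-subject change averaged +0.27.

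**6. Opposing component.** For an assumed decline of 2 to 4 points per year, the loss is rate × days/365.25:

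- untreated 8 to 28 days: 0.04 to 0.31 points
- Day 6 interval of 13 to 36 days: 0.07 to 0.39 points
- nominal Day 33 interval of 40 to 60 days: 0.22 to 0.66 points

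**The case against.** The strongest reply is that the plan already contains the control for this. The SAP 5 sentence that mentions zero goes on to a comparison between groups, and selection acts equally on both randomized arms in expectation. That stands. A reader might infer that the MMSE treatment comparison is biased; the documents do not support this, and step 5 shows no such bias.

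A reader might also infer that MMSE is expected to rise under no effect. That does not follow either. Step 3 holds the true score fixed, whereas Protocol 2.1 describes a progressive disease. At a pool mean of 5 the selection component is +0.05 to +0.34, which an assumed decline of 0.22 to 0.66 points by Day 33 could cancel or exceed. Only the sign of the selection component is known, not that of the net change.

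The size is also open to challenge. The +1.2 end needs a screened mean of 11, above the entry ceiling, in which case about 54% of those screened would fail on MMSE alone. With 11 active evaluable subjects the standard error of the mean change is roughly 0.4 to 1.0 points, and the selection component is below one standard error in all but the most extreme setting. MMSE is one of five descriptive, unpowered secondary efficacy scales, with no test or decision rule attached.

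Finally, a reader might object that the MMSE and SIB Day 6 changes cover different periods. They do, but the plan reports them in separate tables (14.2.1 and 14.2.2) and announces no side-by-side reading.

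What survives is narrower. Zero is still the wrong yardstick for the within-arm and Overall columns, and a placebo group of about 5 evaluable subjects cannot calibrate it: the standard error of its mean change is about e × √2/√5, or 0.6 to 1.6 points for e of 1.0 to 2.5.

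**Conclusion.** The point holds for within-arm and pooled MMSE change. The baseline is the selecting Screening score, and 8 to 28 untreated days sit inside the change; both facts come directly from the documents. The selection component is positive, but its size (about +0.05 to +1.2 points) rests wholly on assumed inputs and is near zero if the screened pool lies well below 10. Progression may offset it, so the documents do not fix the net direction. The between-group comparison is unbiased in expectation. This is a cheap improvement worth making and does not threaten the primary safety objective.

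One related inconsistency matters here. Protocol 7.3.5 lists only SIB and ADCS-CGIC at Visit 8, while table 15.1 and SAP 5.1 include MMSE there, so it is unclear whether the Day 6 MMSE will be collected. The Day 33 change has the same baseline problem either way.

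**What to change.** **For subjects not yet enrolled.** Add MMSE to the Baseline Visit list in Protocol 7.3.2 and mark it at Visit 2 in table 15.1. Use the Screening MMSE for eligibility only, and do not re-apply the 0 to 10 rule at Visit 2. State in SAP 5.1 that the Visit 2 score is the MMSE baseline. The cost is a protocol amendment, a line in the SAP, and one extra short test before dosing at a visit where the subject is already being rated, equal in both arms. Some 1 to 7 untreated days remain.

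**If enrollment is complete, or only some subjects would have a Visit 2 score.** Keep one common reference for all subjects rather than mixing two. Label it Screening in Table 14.2.1, state in SAP 5.1 that within-arm and overall MMSE change will not be interpreted against zero, and rely on the between-group difference. This needs no new data.

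**In either case.** Reconcile Protocol 7.3.5 with table 15.1 and SAP 5.1 on whether MMSE is given at Visit 8.
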